5.6.3.8. Biomicroscopy

Slit-lamp biomicroscopy exam will be performed in each eye.

The number of participants with biomicroscopy findings of any severity increase from baseline at one or more visits will be generated for each MedDRA preferred terms by cohort and study

Safety Statistical Analysis Plan

2012-201-005 [Stage 1]

intervention group for each eye. For findings under "other pathology" which are not associated with a severity grade, a status change from absent to present will be treated as an increase of severity in the analysis.

Table 5-14 Biomicroscopy

Parameter	Description	Timing	Methodology
Biomicroscopy	Any severity increase from baseline for each eye	Treatment period	Categorical descriptives

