1.3. Schedule of Activities (SoA)

Table 1-1 Schedule of Activities – Stage 1

Study Day (Unless otherwise specified, all examinations/procedures for a	Visit 1 Screening	Visit 2 (Baseline)	Visit 3	Visit 4	Visit 5 (Exit) or Early Termination	
timepoint must be performed in the order listed below)	Day -14 to Day -1	Day 1	Day 2	Day 8 (+1)	Day 15 (+2)	Notes
Informed consent	X					
Inclusion and exclusion criteria	X	X				Recheck participant eligibility before randomization and/or first dose of study intervention.
Demographics	X					
Medical, ophthalmic, and surgical history (includes substance usage)	X	X				
Prior or concomitant medication review	←=====				→	
AE review	←=====				-	
Vital signs (RR, height, and weight)	X				X	Height measurement will not be performed at Visit 5 or the Early Termination visit.
Vital signs (blood pressure, pulse rate, and temperature)	X	X	X	X	X	
Physical examination	X				X	
12-lead ECG	X				X	At the Exit visit, ECG will be performed at 0 hour (predose) and 45 ± 15 minutes postdose.
Pregnancy test (WOCBP only)	X	X			X	Serum pregnancy test will be performed at Screening; at all other indicated visits, serum or urine pregnancy test will be performed.
Drugs of abuse screen	X	X				Breathalyzer may be used for alcohol.
Hematology, chemistry, and urinalysis	X				X	Participants will be instructed to fast (ie, water only) for at least 10 hours prior to blood collection for safety laboratory tests.
Serology	X					

			Interv	ention Period		
Study Day (Unless otherwise specified, all examinations/procedures for a	Visit 1 Screening	Visit 2 (Baseline)	Visit 3	Visit 4	Visit 5 (Exit) or Early Termination	
timepoint must be performed in the order listed below)	Day -14 to Day -1	Day 1	Day 2	Day 8 (+1)	Day 15 (+2)	Notes
	X	X				
Manifest refraction	X	X	X	X	X	
Best-corrected visual acuity	X	X	X	X	X	
Slit lamp biomicroscopy	X	X	X	X	X	
	X	X				
	X	X				
Intraocular pressure	X	X	X	X	X	
Dilated fundus exam	X				X	
Randomization		X				
Blood sample collection for PK analysis		X	X	х	X	Blood samples for PK analysis will be collected at Visit 2 at 0 hour (predose) and at Visits 3 and 5 at 0 hour (predose) and 0.5, 1, 2, 4, 8, and 12 hours postdose. In addition, at Visit 4, a sample will be collected at 0 hour (predose) and at 0.5 hours postdose. At Early Termination visit, only a single sample will be collected. For the full blood sample collection schedule, refer to Table 8-12.

			Interv	ention Period		

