Study Day (Unless otherwise specified, all examinations/procedures for a	Visit 1 Screening	Visit 2 (Baseline)	Visit 3	Visit 4	Visit 5 (Exit) or Early Termination	
timepoint must be performed in the order listed below)	Day -14 to Day -1	Day 1	Day 2	Day 8 (+1)	Day 15 (+2)	Notes
Tear sample collection for PK analysis			X	X	X	Tear samples for PK analysis will be collected at Visits 3 and 5 at 0 hour (predose) and 0.5, 2, 4, 8, and 12 hours postdose. In addition, at Visit 4, a sample will be collected at 0.5 hours postdose. Tear samples will be collected from both eyes. For the full tear sample collection schedule, refer to Table 8-14. Tear collection will not be performed at the Early Termination visit.
Administration of study intervention		X	X	X	X	Study interventions will be administered as a single drop to the left eye on Day 1 and as a single drop to both eyes, twice daily (approximately 12 hours apart) for 13 days (Days 2-14), followed by a single dose administration to both eyes on Day 15. The morning dose will be administered by site staff on visit days. Dosing will not be performed at the Early Termination visit.
Drop Tolerability Questionnaire		X	X	X	X	Drop Tolerability Questionnaire must be administered within approximately 5 minutes following morning administration of study intervention. Drop Tolerability Questionnaire will not be administered at the Early Termination visit.
Dispensing of study intervention to participant			X	X		
Collection of used and unused study intervention		DV 1	1:	X	X	

AE = adverse event; ECG = electrocardiogram;

; PK = pharmacokinetic; RR = respiration rate; WOCBP = women of childbearing potential

[figure not shown]

Table 1-2 Schedule of Activities – Stage 2

Study Day						Intouron	tion Period	 			
Unless otherwise specified with a '#', all		it 1 ening	Visit 2		sit 3 eline)	Visit 4	Visit 5	Vis (E:	sit 6 xit)	Early Termination	Notes
examinations/procedures for a timepoint will be		4 days Visit 2	Day -14 (± 2)	Da	ıy 1	Day 14 (± 2)	Day 28 (± 3)		y 42 : 5)	NA	
performed in the order listed below*	Pre- CAE	Post- CAE	NA	Pre- CAE	Post- CAE	NA	NA	Pre- CAE	Post- CAE	NA	
Informed consent	X										
Inclusion and exclusion criteria	X	X		X	X						Recheck participant eligibility before randomization and/or first dose of study intervention
Demographics #	X										
Medical, ophthalmic, and surgical history (includes substance usage) #	Х		X	Х							

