4.2. Scientific Rationale for Study Design

4.2.1. Duration of Treatment in Stage 1 and Stage 2

In Stage 1, on Day 1 participants will receive a single drop of the intervention to the left eye only. Starting on Day 2, the participants will administer a single drop to both eyes twice daily (approximately 12 hours apart) for additional 13 days (through Day 14), followed by a single dose administration to both eyes on Day 15. Two weeks of administration was estimated to be sufficient to evaluate safety and tolerability of each dose level.

In Stage 2, participants will administer a single drop of the assigned intervention to both eyes twice daily (approximately 12 hours apart) for 41 days, followed by a single dose administration to both eyes on Day 42. Based on the pharmacology of AGN-242428 and AGN-231868, 6 weeks of twice daily treatment is expected to provide sufficient time to improve the signs and/or symptoms of DED.

4.2.2. Cohorts in Stage 1

Up to 3 cohorts are planned in Stage 1. Cohort 1A will be the lowest dose cohort. Once Cohort 1A is completed, the DMC will review the data and provide recommendation if the study should proceed to Cohort 1B (high dose). Following completion of Cohort 1B, the DMC will review the data, and in the event that any concerning safety and/or tolerability findings are identified, the study may proceed to Cohort 1C (mid dose). If no safety concerns are identified in Cohort 1B, Cohort 1C will not be conducted and the study will proceed to Stage 2. This design

will allow for identification of the highest tolerated/feasible dose of each intervention to proceed to Stage 2.

It is possible that only 1 of the 2 tested experimental interventions (AGN-242428 or AGN-231868) and its vehicle will proceed to the next cohort based on the safety data review.

4.2.3. Dose Selection for Stage 2

AGN-242428 and AGN-231868 dose levels in Stage 2 will be selected by the sponsor based on the data from Stage 1. The highest tolerated dose of each intervention (established in Stage 1) will be selected for testing in Stage 2 to maximize the potential to achieve proof of concept. It is possible that only 1 experimental intervention (AGN-242428 or AGN-231868) will have acceptable safety to proceed to Stage 2.

[figure not shown]

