6.1.1. Dosing Regimen

6.1.1.1. Dosing Regimen in Stage 1

Stage 1 includes up to 3 consecutive cohorts, with 24 participants in each cohort. Participants from 1 cohort will not be allowed to enroll into the subsequent cohort(s). Participants in each cohort will be randomized into 1 of 4 intervention arms:

- AGN-242428 (N = 9)
- AGN-231868 (N = 9)
- AGN-242428 vehicle (N = 3)
- AGN-231868 vehicle (N = 3)

The morning dose of the assigned study intervention will be administered by the site staff at Visits 2, 3, 4, and 5 (except for Early Termination visit).

All participants will receive 1 drop of the assigned intervention to the left eye on Day 1 (Visit 2) (administered by the site staff). On Days 2 to 14, the participants will administer a single drop to both eyes, twice daily (approximately 12 hours apart). On Day 15 (Visit 5), the participants will be administered a single dose to both eyes.

6.1.1.2. Dosing Regimen in Stage 2

In Stage 2,

approximately 250 participants, who requalify at Baseline visit, will be randomized into 5 groups, in a 1:1:1:1:1 ratio within each site, as follows:

- AGN-242428 (N = 50)
- AGN-242428 vehicle (N = 50)
- AGN-231868 (N = 50)
- AGN-231868 vehicle (N = 50)
- Xiidra (N = 50)

The morning dose of the assigned study intervention will be administered by the unmasked site staff at Visits 2, 3, 4, 5, and 6. Any masked staff members should not be present in the room during dosing to prevent unmasking.

During the intervention period, participants will be instructed to administer 1 drop of assigned intervention twice daily (approximately 12 hours apart) to both eyes on Days 1 to 41. On Day 42, the participants will be administered a single dose to both eyes. The highest tolerated doses of AGN-242428 and AGN-231868 (established in Stage 1) will be selected for testing in Stage 2 to maximize the potential to achieve proof of concept.

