- WHO Drug Dictionary will be used to code medications.
- Relative study day is defined as the number of days from the first dose date and will be presented in all data listings where a complete date is presented.
- The baseline for safety parameters will be the last assessment prior to the first administration of study intervention.
- Day 1 is the study day on which study intervention is first administered.
- The end of study for a participant is the last date that he/she participated in the study. The date will be captured on the end of intervention eCRF page.

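### Stage 1: the right eye's Day 2 slit-lamp exam comes before its first drop, yet the SAP counts it as a treatment-period finding (minor)

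*SAP*

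**What the plan says.** **Dosing.** Protocol section 4.2.1 says that "on Day 1 participants will receive a single drop of the intervention to the left eye only". Section 6.1.1.1 continues: "On Days 2 to 14, the participants will administer a single drop to both eyes, twice daily". The notes to Table 1-1 add: "The morning dose will be administered by site staff on visit days". The first right-eye drop is therefore given at the site during Visit 3.

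**Order within a visit.** Table 1-1 says that, unless otherwise specified, procedures "must be performed in the order listed below". BCVA, slit lamp and IOP stand above the row for administering study drug. The ECG and PK rows carry notes asking for postdose measurements; the three ocular rows do not.

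**Baseline.** Stage 1 SAP section 5.1: "The baseline for safety parameters will be the last assessment prior to the first administration of study intervention". Study day (Table 6-8) also runs from the participant's first dose, and Table 6-9 assigns Days 2 to 5 to Visit 3. No rule is specific to an eye.

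**Summaries.** Section 5.6.3.8 is the count at issue: "The number of participants with biomicroscopy findings of any severity increase from baseline at one or more visits will be generated", by cohort, arm and eye, with the treatment period as its timing. BCVA (5.6.3.6) and IOP (5.6.3.7) are instead presented at each postbaseline visit for each eye. Section 5.1 promises listings of all data.

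**The concern.** The biomicroscopy table reports each eye separately, so a reader will take the right-eye row as findings in a treated eye. Under the rules above, the row also contains an exam of an eye that had received nothing. Because visits are pooled, the table cannot show whether a right-eye finding came from that exam or from a later one.

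The threshold is any increase, which on the slit-lamp scales in Protocol section 8.1.2 includes a step of half a grade, so the count is open to grading noise. Arms are small: one stray finding in a vehicle arm of 3 reads as 33%. Ocular safety is a primary Stage 1 objective, and this is its planned slit-lamp summary.

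Day 2 is also the only scheduled exam at which one eye has been dosed and its fellow has not. No left-versus-right summary is planned there.

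**Working it through.** **1. Plan's own figures.** 24 × 3/8 = 9 per active arm and 24 × 1/8 = 3 per vehicle arm. Three cohorts give 3 × 24 = 72. These reproduce. Stage 1 has no power calculation or test to check.

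**2. Exams by each eye's dosing status.**

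| Scheduled exam | Left eye | Right eye | SAP status, both eyes |
|---|---|---|---|
| Day 1, predose | undosed | undosed | baseline |
| Day 2, predose | dosed | undosed | postbaseline |
| Day 8 | dosed | dosed | postbaseline |
| Day 15 | dosed | dosed | postbaseline |

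For the right eye, 1 of 3 postbaseline exams precedes its first dose. That is 24 of 72 right-eye exams per full cohort, or 72 of 216 if all three cohorts run.

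**3. Effect on the count.** The documents give no background rate, so let *p* be an assumed chance of any upward change per eye per visit.

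- Independent visits, as planned: 1 − (1 − *p*)³. Own-dose exams only: 1 − (1 − *p*)². The excess is *p*(1 − *p*)².
- Within-eye correlation 0.5 (beta-binomial): the chance of no change is (1 − *p*)(2 − *p*)/2 over two visits, and that times (3 − *p*)/3 over three. The excess is [(1 − *p*)(2 − *p*)/2] × *p*/3.

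| *p* | As planned | Own-dose exams | Excess per 9, independent | Excess per 9, correlation 0.5 |
|---|---|---|---|---|
| 2% | 5.9% | 4.0% | 0.17 | 0.06 |
| 5% | 14.3% | 9.8% | 0.41 | 0.14 |
| 10% | 27.1% | 19.0% | 0.73 | 0.26 |

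In a vehicle arm of 3, the independent excess is 0.06, 0.14 and 0.24. Under independence *p*(1 − *p*)² peaks at *p* = 1/3, at 4/27, so the excess cannot pass 9 × 4/27 = 1.33 participants per arm of 9 at any rate. With perfect correlation it is zero. All three changes subtract the same Day 1 reading, so positive correlation is likely and the independent column is best read as the high end.

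**4. What a Day 2 fellow-eye contrast could add.** Take a continuous measure with change SD 1 and an assumed inter-eye correlation ρ of 0.5, 0.6 or 0.8.

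- Active versus vehicle, one eye: √(1/9 + 1/3) = 0.67 SD.
- Left minus right within 9 active participants: √(2(1 − ρ)/9) = 0.33, 0.30 or 0.21 SD. This estimates drop versus no drop.
- Active minus vehicle in the left-minus-right change: √(2(1 − ρ)(1/9 + 1/3)) = 0.67, 0.60 or 0.42 SD.

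Only the first and third lines address drug versus vehicle. Their ratio is 1.0, 1.1 or 1.6.

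**The case against.** The best defence is that a participant-level baseline is the inclusive choice in a first-in-human study. It keeps any effect of the Day 1 drop that reaches the other eye, and it matches the SAP's rule for treatment-emergent adverse events. Stage 1 is descriptive, and the listings let a careful reader recover Day 2 findings by eye. This is a sound reason to keep the Day 1 baseline. It does not justify a per-eye, treatment-period count that hides which right-eye findings came before any drop in that eye.

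Several stronger readings are tempting, and the documents do not support them:

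- *The error also distorts BCVA and IOP.* Both are shown by visit and eye, so the Day 2 right-eye values stand apart. Only their status as postbaseline, treatment-period values is inexact.
- *The fellow-eye control is thrown away.* For BCVA and IOP it is displayed but not compared; for slit lamp it remains in the listings.
- *The drug is made to look worse than vehicle.* The extra exam occurs in every arm. It adds noise and dilution, not a systematic difference.
- *These tables decide the Stage 2 dose.* Cohort progression follows DMC review of safety data, and Protocol section 9.5 says the interim analysis results are not needed to proceed to Stage 2.
- *The paired contrast is 2.0 to 3.2 times as precise as active versus vehicle.* That ratio sets drop versus no drop against drug versus vehicle. Like for like, the gain is 1.0 to 1.6 times, and slit-lamp grades are ordinal, so even this is approximate.

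**Conclusion.** The right-eye biomicroscopy rule is wrong as written, and the matter is minor. The misclassification follows from the dosing schedule, the fixed visit order and the baseline rule, and needs no assumed rate. Its size does: about 0.2 to 0.7 participants per arm of 9 at background rates of 2% to 10% with independent visits, falling to zero as within-eye correlation becomes perfect.

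The conclusion takes 'each eye' to mean right and left, since the legible text defines no clear study eye for Stage 1. It also assumes that sites followed the Table 1-1 order, and that this order, read here from protocol Amendment 3, matches Amendment 2, on which the Stage 1 SAP is based. A related case is a participant who stops after the Day 1 dose: the right eye is never dosed, yet any Early Termination exam of it would enter the same row.

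**What to change.** 1. Keep the Day 1 baseline for both eyes. In section 5.6.3.8, count a right-eye exam as on-treatment only if it follows that eye's own first dose, judged by date and time. Do not exclude the whole Visit 3 window: it runs through Day 5, and section 6.4.2 provides for repeated and unscheduled exams, so a right-eye exam after the Day 2 dose must still count. Where no clock time was recorded, treat the scheduled Visit 3 exam as predose, following the schedule.
2. Alternatively, tabulate biomicroscopy by visit and eye, and label the right-eye Day 2 predose exam as before first dose in this eye.
3. Add a descriptive Day 2 left-versus-right summary of change from Day 1, by cohort and arm, for slit-lamp grades, IOP and BCVA. State that within an arm it estimates drop versus no drop, and that drug versus vehicle needs the difference between arms.
4. Footnote the Day 2 right-eye rows of the BCVA and IOP tables in the same way.

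The cost is a little reprogramming of existing data; dosing and visit procedures do not change. Stage 2 SAP section 10.0 records that Stage 1 has been locked, unmasked and analysed, so the new outputs must be labelled supplementary or post hoc.

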5.6.3.9. Dilated Fundus Examination

Lens, vitreous, fundus, and optic nerve will be evaluated for pathology. If pathology is present, it will be recorded.

Cup/disc ratio will be reported using 0.0 to 1.0 scale according to an Armaly chart. Lens status will be assessed as phakic, pseudophakic, or aphakic. Cataract assessment for presence and severity of nuclear, cortical and posterior subcapsular cataract lens opacities will be evaluated. Each type of cataract severity and change from baseline will be evaluated. These data will be presented as listings only.

Table 5-15 Dilated Fundus Examination

Parameter	Description	Timing	Methodology
Dilated Fundus Examination	Listing for the following data: Cup/disc ratio Lens status Cataract assessment	Treatment period	Listing

5.6.3.10. Drop Tolerability Questionnaire Score

Participants will be asked to rate the acute overall tolerability attributes of study interventions on an 8-question VAS Drop Tolerability Questionnaire. Descriptive statistics for each question at Baseline (Day 1), and changes from baseline at each postbaseline visit will be presented by cohort and study intervention group.

Table 5-16 Drop Tolerability Questionnaire Score

Parameter	Description	Timing	Methodology
Drop Tolerability Questionnaire VAS	Raw values and change from baseline	Treatment period	CFB descriptives
score			

Safety Statistical Analysis Plan 2012-201-005 [Stage 1]

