7.2. Participant Discontinuation/Withdrawal from the Study

- A participant may withdraw from the study at any time at his/her own request or may be withdrawn at any time at the discretion of the investigator for safety, behavioral, compliance, or administrative reasons.
- Participants may be discontinued at the discretion of the investigator and/or the sponsor if they use any prohibited treatments described in Section 6.5.4.
- For participants who discontinue from the study early, every effort must be made to have these participants return to the clinical center for completion of the Early Termination visit. AEs leading to participant early discontinuation must be followed-up as appropriate.
- If the participant withdraws consent for disclosure of future information, the sponsor may retain and continue to use any data collected before such a withdrawal of consent.
- See the SoA (Section 1.3) for data to be collected at the time of study discontinuation (Early Termination). If the Early Termination visit falls on the same day as another scheduled visit, only Early Termination visit assessments will be conducted.
- Study termination

The dosing of study intervention may be paused due to safety concerns at any time by the site investigator. The sponsor and DMC must be notified immediately if the dosing was paused.

The sponsor may stop the study (and/or the study site) for any reason with appropriate notification.

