5.1. General Considerations

The methodologies specified to individual variables are defined as follows:

Table 5-1 Statistical Methodology

Methodology	Description
Categorical descriptives	 Number and percentage of participants in individual categories ○ Participants with ≥ 1 qualifying event counted once per individual category
PCS descriptives	 Number and percentage of participants meeting potentially clinically significant (PCS) criteria ○ Participants with ≥ 1 qualifying event counted once per PCS category Percentage denominator = number of participants with available (non-missing) non-PCS baseline value(s) or available (non-missing) baseline and ≥1 non-missing postbaseline assessment ○ Unevaluable assessments considered missing
Continuous descriptives	 N1, mean, standard deviation (SD), Q1, Q3, median, minimum, maximum N1 = participants with non-missing value
CFB descriptives	 Continuous descriptives for baseline, postbaseline, and change from baseline (CFB) values N1 = participants with non-missing values at both baseline and the specified postbaseline analysis by visit/timepoint
Supportive data listing	 After table listings, i.e. the listing supports the findings from a table. Fully defined in the tables, figure, and listing specification document

CFB = change from baseline; PCS = potentially clinically significant; SD = standard deviation.

- An interim database lock will occur after completion of Stage 1. At the end of the study (completion of Stage 2), the final database lock will occur.
- All data will be provided in data listings which will be fully defined in the table, figure, and listing specification document. For these data listings, missing or incomplete dates or missing AE severity or relationship will be listed as is.
- The change from baseline values will be computed as the value for the post baseline visit minus the baseline value, unless otherwise indicated.
- Safety analyses will be based on the observed data. No imputation of missing values will be performed.

Safety Statistical Analysis Plan 2012-201-005 [Stage 1]

- Partial dates will be treated as missing in computations but will be listed in the data listings as they appear on the eCRFs unless otherwise specified. No imputation of missing values will be performed, unless otherwise specified.
- All statistical analysis will be performed using SAS version 9.4 or higher.
- MedDRA will be used to code adverse events and medical history.

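### Stage 1 drop tolerability is summarised only by visit in those still being dosed, so participants who leave for intolerability are absent from the later raw-value rows

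*SAP*

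**What the plan says.** Table 1-1 of the Stage 1 SAP lists the Drop Tolerability Questionnaire score among the primary safety variables. Section 5.6.3.10 gives its whole analysis: "Descriptive statistics for each question at Baseline (Day 1), and changes from baseline at each postbaseline visit will be presented by cohort and study intervention". Table 5-16 assigns it the change-from-baseline method. Table 5-1 (Section 5.1) defines that method as baseline, post-baseline and change values, with "N1 = participants with non-missing values at both baseline and the specified postbaseline analysis by visit/timepoint". Section 5.1 also states: "Safety analyses will be based on the observed data. No imputation of missing values will be performed".

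Protocol Table 1-1 (Section 1.3) schedules the questionnaire on Days 1, 2, 8 and 15, shortly after the morning drop. For those who leave, it states that "Drop Tolerability Questionnaire will not be administered at the Early Termination visit" and that "Dosing will not be performed at the Early Termination visit". Protocol Section 7.2 adds: "If the Early Termination visit falls on the same day as another scheduled visit, only Early Termination visit assessments will be conducted".

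No worst-score or any-visit summary of the questionnaire is planned. Other Stage 1 safety measures have one. Section 5.6.3.8 tabulates "The number of participants with biomicroscopy findings of any severity increase from baseline at one or more visits". Sections 5.6.3.1, 5.6.3.3 and 5.6.3.4 count participants with at least one potentially clinically significant post-baseline laboratory, vital sign or ECG value.

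**The concern.** The objective is tolerability in treated participants. A questionnaire score exists only if a drop was given in clinic at that visit. A participant who stops because of burning, stinging or blur therefore has no later score, and the reason for the gap is the outcome being measured. The Day 8 and Day 15 raw levels then answer a narrower question: how the drops feel to those who carried on.

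At stake is how a primary tolerability endpoint reads in small arms. If leaving for intolerability is more common in an active arm than in its vehicle, the later rows would understate the difference between them.

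**Working it through.** **Is there a figure to reproduce?** No. Stage 1 SAP Section 3 calls the sample size empirical, and no dropout rate, score mean or SD is given. The allocation arithmetic agrees with the documents: 24 × 3/8 = 9 per active arm, 24 × 1/8 = 3 per vehicle arm, and 3 cohorts × 24 = 72.

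**Who is in each row?** Take a participant who stops between Day 2 and Day 8. The Day 1 and Day 2 scores exist; the Day 8 and Day 15 scores do not. If the Early Termination visit falls on Day 8 itself, the Section 7.2 rule means the Day 8 score is not taken either.

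**Shift in a later raw mean.** Let n be the arm size, k the number of leavers, S the mean of those who stay, and g the amount by which leavers would have scored worse.

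- Full-arm mean = [(n − k)·S + k·(S + g)]/n = S + k·g/n
- Observed mean = S
- Shift towards better tolerability = k·g/n

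The arm sizes are the plan's. The gaps of 20, 40 and 60 mm on the 100 mm scale are assumptions.

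| n | k | g = 20 | g = 40 | g = 60 |
|---|---|---|---|---|
| 9 | 0 | 0 | 0 | 0 |
| 9 | 1 | 2.2 mm | 4.4 mm | 6.7 mm |
| 9 | 2 | 4.4 mm | 8.9 mm | 13.3 mm |
| 9 | 3 | 6.7 mm | 13.3 mm | 20.0 mm |
| 3 | 1 | 6.7 mm | 13.3 mm | 20.0 mm |

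**Chance of at least one leaver in an arm of 9.** This is 1 − (1 − p)⁹. At assumed leaving rates of 5%, 10% and 20% it is 37%, 61% and 87%. These are rates of leaving for intolerability, and the documents support none of them in particular.

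**Does the paired change mislead?** Suppose one leaver scores 70 on Day 1 and would score 70 on Day 15, and eight stayers score 15 on both days.

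- Day 1 raw mean, all nine: (70 + 8 × 15)/9 = 21.1
- Day 15 raw mean, eight stayers: 15
- Planned Day 15 change, eight paired participants: 15 − 15 = 0
- Full-arm change: 0

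The planned change is correct here. It would be wrong only if the leaver's trajectory differed from the stayers'. But a change of 0 does not show that one participant in nine found the drops hard to tolerate. The Day 1 reference was itself scored after a drop (one drop, left eye only), so steady intolerance gives a change near zero.

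**The case against.** The case on the other side is substantial, and most of it narrows the point.

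- **The apparent time trend.** A reader might infer that a dose could seem to become better tolerated over time only because the worst-affected left. The planned change analysis does not do this, because it pairs the same participants. A false trend appears only if raw rows with different N1 are compared, as with 21.1 against 15 above, and N1 is shown.
- **Dose choice.** A reader might also infer that the Day 15 mean drives the Stage 2 dose. Protocol Section 4.2.3 does say that "The highest tolerated dose of each intervention (established in Stage 1) will be selected for testing in Stage 2", but it names no Day 15 mean. Protocol Section 9.5 says the interim results are not needed to proceed to Stage 2. Under Protocol Section 10.1.11, cohort decisions follow committee review of safety data, with details in a charter that is not among the documents. The inference is not supported.
- **More than means is planned.** Table 5-1 includes minimum, maximum and quartiles, so an extreme score given at an attended visit is visible. It is not followed per participant, and it too is absent from rows after the participant leaves.
- **Leavers appear elsewhere.** Section 5.2 gives discontinuation reasons by arm, Table 5-4 counts adverse events leading to discontinuation, and all data are listed. This stands, but none of these outputs summarises leavers' questionnaire scores. The separate discontinuation table by system organ class and preferred term is produced only if at least 5 participants report such events. Protocol Section 1.1 also allows replacement after withdrawals not due to adverse events, so N1 may not fall visibly.
- **A worst score is not a cure.** It uses only scores already given. A leaver has one to three assessments and a completer has four, so leavers may still look milder. This stands.

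**Conclusion.** The gap is real but limited. The only planned questionnaire summary is by visit, in participants scored at that visit, so the later raw levels omit anyone who left for intolerability. The paired change rows are sound under similar trajectories but do not describe the level of tolerability.

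The size cannot be determined from the documents. The table above depends entirely on assumed gaps and numbers of leavers, and the shift is nil if nobody leaves early. The consequence that can be supported is for reporting of a primary tolerability endpoint in a descriptive stage without hypothesis testing. An effect on the Stage 2 dose is not shown.

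**What to change.** In Stage 1 SAP Section 5.6.3.10, add a supplementary summary by cohort and intervention for the whole Safety Population: each participant's worst post-dose score per question over all assessments. Define worst by item direction:

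- maximum for stickiness, blur, burning/stinging and discomfort;
- minimum for comfort, soothing, moistening/lubricating and clarity of vision.

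Place beside it the number in each arm who discontinued early, with reasons. Keep the by-visit rows as planned.

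The cost is SAP wording and one table from scores already scheduled, including a Day 1 post-dose score for every participant. No visit or treatment procedure changes. The SAP should state two downsides. Worst scores rise with the number of assessments, so the table reduces the bias without removing it, and active arms should be read against vehicle. Section 10.0 of the Stage 2 SAP reports that the Stage 1 lock, unmasking and analyses have taken place, so a table added after that point should be labelled post hoc.
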